### **12.2 Participant demographics and other baseline characteristics**

Demographic and other baseline data including disease characteristics will be listed and summarized descriptively by treatment group and cohort for the safety analysis set.

Categorical data will be presented as frequencies and percentages. For continuous data, mean, standard deviation, median, minimum, and maximum will be presented.

Relevant medical histories and current medical conditions at baseline will be summarized by system organ class and preferred term by treatment group and cohort.

### **12.3 Treatments**

Concomitant medications and significant non-drug therapies prior to and after the start of the study treatment will be listed and summarized according to the Anatomical Therapeutic Chemical (ATC) classification system by treatment group and cohort.

### **12.4 Analysis of the primary endpoint(s)/estimand(s)**

#### **12.4.1 Definition of primary endpoint(s)/estimand(s)**

The primary endpoint will be conversion to sinus rhythm for at least one minute within 90 minutes after the start of study drug administration (yes or no).

#### **12.4.2 Statistical model, hypothesis, and method of analysis**

The conversion rates between HSY244 and placebo will be compared using Fisher's Exact test. This will test a null hypothesis that the conversion rate is the same for HSY244 and placebo. The difference in the conversion rates between HSY244 and placebo will be reported along with the 80% confidence limits for the difference, as well as the odds ratio, the 80% CI for the odds ratio, and the associated p-value.

Results will be displayed tabular and graphically, where the conversion rate (80% CI) for each treatment will be displayed in dot plots and a forest plot.

The impact of duration of current atrial fibrillation episode (< 48 hours, 48 hours - 7 days, 7 - 14 days, 14 - 30 days, and 30 - 60 days) on conversion rate will be investigated in a supporting analysis..

Commercially Confidential Information

Only participants who complete study treatment will be included in the primary analysis.

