## **9 Study discontinuation and completion**

### **9.1 Discontinuation and completion**

#### **9.1.1 Study treatment discontinuation and study discontinuation**

The Investigator must discontinue study treatment for a given participant if, he/she believes that continuation would negatively impact the participant's well-being.

Study drug administration must be discontinued under the following circumstances:

- Participant withdraws consent
- Development of new complete bundle branch block (QRS duration >120ms) for a participant with a normal QRS duration at baseline as determined by the Investigator's interpretation of the ECG findings or an increase in QRS duration that in the opinion of the Investigator may be a risk to participant safety
- QTcF >500 ms for those individuals with a normal QTcF at baseline as determined by the Investigator's interpretation of the ECG findings, or an increase in QTcF that in the opinion of the Investigator may be a risk to participant safety
- A change in atrioventricular conduction that in the opinion of the Investigator may be a risk to participant safety
- An increase in the resting heart rate to >130 beats per minute sustained for >2 minutes as determined by the Investigator, unless there is an obvious alternative explanation other than administration of study drug
- Hypotension, defined as >20 mmHg systolic blood pressure drop (repeat measurement) that is (a) symptomatic or (b) sustained to the point requiring medical intervention
- Any moderate or higher CNS-related AE that in the opinion of the Investigator is suspected to be related to the study drug
- A seizure
- A severe or serious adverse event
- Hypersensitivity reactions and/or injection site reactions of moderate severity or greater

If discontinuation of study drug administration occurs, the investigator should make a reasonable effort to understand the primary reason for the participant's premature discontinuation of study drug administration and record this information.

Participants who discontinue study drug administration or who decide they do not wish to participate in the study further should NOT be considered withdrawn from the study UNLESS they withdraw their consent (see 'Withdrawal of Informed Consent' [Section 9.2](#)).

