#### **12.4.4 Handling of missing values not related to intercurrent event**

Given the short treatment duration in this study, missing data impacting the primary endpoint is expected to be minimal. All participants who complete Day 1 assessments will be included in the primary analysis.

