6.1.1 Variables

The primary endpoint will be conversion to sinus rhythm for at least one minute within 90 minutes after the start of study drug administration (yes or no). Only participants that complete treatment will be included in the primary analysis. If a participant has been monitored for at least 45 minutes and is not converted to sinus rhythm, the primary endpoint will be defined as

| Novartis | For business use only | Page 9 |
|----------|-----------------------|--------------|
| SAP | | CHSY244X2201 |

'no'. If a participant converts to sinus rhythm at any time during the post-treatment 90 minutes observation period, regardless of the length of time monitored, the primary endpoint will be defined as 'yes'. Participants with a non-missing primary endpoint value will be included in the primary analysis regardless of their study disposition e.g. loss to follow up, early termination, etc.

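### The primary analysis keeps only participants who finish the infusion, so it drops observable outcomes after a post-randomisation stop, and Protocol 12.4.4 gives a different inclusion rule

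*Protocol*

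**What the plan says.** Four places in the visible text decide who enters the primary comparison.

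- **Protocol 12.4.2:** "Only participants who complete study treatment will be included in the primary analysis". SAP 6.1.3 repeats the sentence.
- **Protocol 12.4.4**, on missing values: "All participants who complete Day 1 assessments will be included in the primary analysis".
- **SAP 6.1.1:** "Only participants that complete treatment will be included in the primary analysis". Later in the same paragraph: "Participants with a non-missing primary endpoint value will be included in the primary analysis regardless of their study disposition".
- **Protocol 12.4.6:** a supplementary Fisher's exact test on everyone who received any study drug.

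SAP 6.1.1 also sets the scoring. The endpoint is 'no' under this condition: "If a participant has been monitored for at least 45 minutes and is not converted to sinus rhythm". It is 'yes' under this one: "If a participant converts to sinus rhythm at any time during the post-treatment 90 minutes observation period, regardless of the length of time monitored".

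Protocol 9.1.1 lists ten circumstances in which the infusion must be stopped. One is withdrawal of consent. The other nine are safety events, for example: "Any moderate or higher CNS-related AE that in the opinion of the Investigator is suspected to be related to the study drug". Participants who stop "should NOT be considered withdrawn from the study UNLESS they withdraw their consent". Section 3 keeps the study Holter on for 24 hours, and the endpoint window runs for 90 minutes from the start of administration, not from its completion. Section 9.1.2 replaces participants who stop early, except those who stopped for adverse drug reactions or adverse events from study procedures. Protocol 12.4.3 (intercurrent events) and 12.4.5 (sensitivity analyses) are both marked not applicable.

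**The concern.** Randomisation makes the arms comparable as assigned. Selecting on whether the infusion was finished selects on something that happens afterwards and that the drug can influence. The protocol gives grounds to expect this. Section 4.5.1 describes reversible CNS symptoms with another GIRK1/4 inhibitor, and Section 4.5.2 describes higher resting heart rates in GIRK4-deficient mice. CNS events and heart rate are both stopping criteria.

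The excluded outcomes are for the most part not missing. They can be read from the same Holter trace as everyone else's. Participants stopped for drug reactions are neither analysed in the primary comparison nor replaced.

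The second problem is that the rule is not the same throughout. Two analysts who follow different sections could report different primary denominators.

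The third is that the 45-minute condition makes inclusion depend on outcome. Among participants monitored for less than 45 minutes, converters count and non-converters have no value in the visible text.

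**Working it through.** **Inclusion rules side by side**

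| Participant | Protocol 12.4.2, SAP 6.1.1 and 6.1.3 | Protocol 12.4.4 | Protocol 12.4.6 (supplementary) |
|---|---|---|---|
| Finishes infusion and Day 1 assessments | in | in | in |
| Infusion stopped early, finishes Day 1 assessments | out | in | in |
| Finishes infusion, misses part of Day 1 | not excluded | not covered | in |

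The two SAP 6.1.1 sentences can be read together as treatment completers with a non-missing endpoint. The conflict is therefore between Protocol 12.4.2 with the SAP on one side and Protocol 12.4.4 on the other.

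**Inputs for an illustration**

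No planned figure can be reproduced, because the sample size section is redacted. The protocol gives about 29 randomised in Cohort 1, about 20 of them on HSY244, at 5:1. These do not fit one split on the visible text: 29 × 5/6 = 24.2, while 20 × 6/5 = 24 in total. I therefore show 24 vs 5, 20 vs 4, and the literal 20 vs 9 (29 − 20 = 9). All conversion and stopping counts are assumed. The visible text sets no alpha, so 0.05 is only a familiar marker.

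**Method:** rate = converters / analysed; two-sided Fisher's exact test; Clopper-Pearson 80% CI.

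| Split, placebo | All dosed | Drop stopped non-converters | Drop stopped converters |
|---|---|---|---|
| 24 vs 5, 0/5 | 12/24 = 50.0%, p = 0.059 | two: 12/22 = 54.5%, p = 0.047 | two: 10/22 = 45.5%, p = 0.124 |
| 24 vs 5, 1/5 | 12/24 = 50.0%, p = 0.343 | two: 12/22 = 54.5%, p = 0.326 | two: 10/22 = 45.5%, p = 0.619 |
| 20 vs 4, 0/4 | 10/20 = 50.0%, p = 0.114 | two: 10/18 = 55.6%, p = 0.096 | two: 8/18 = 44.4%, p = 0.254 |
| 20 vs 4, 1/4 | 10/20 = 50.0%, p = 0.596 | two: 10/18 = 55.6%, p = 0.587 | two: 8/18 = 44.4%, p = 0.616 |
| 20 vs 9, 1/9 | 10/20 = 50.0%, p = 0.096 | one: 10/19 = 52.6%, p = 0.049 | one: 9/19 = 47.4%, p = 0.098 |

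**Shift in the HSY244 rate from two exclusions**

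Formulas: x/(n−2) − x/n if the two did not convert; (x−2)/(n−2) − x/n if they did.

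| n | x/n = 25% | x/n = 50% | x/n = 75% |
|---|---|---|---|
| 24 | +2.3 / −6.8 points | +4.5 / −4.5 | +6.8 / −2.3 |
| 20 | +2.8 / −8.3 | +5.6 / −5.6 | +8.3 / −2.8 |

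For scale, the 80% CI is 35.3 to 64.7% at 12/24 and 33.8 to 66.2% at 10/20, a half-width of about 15 to 16 points.

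**45-minute rule**

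Take 24 dosed, 12 converters, and one non-converter monitored for under 45 minutes. Scored 'no', the rate is 12/24 = 50.0%. Left without a value, it is 12/23 = 52.2%. Because only non-converters can be lost this way, the rule can only raise the rate in the arm where it operates.

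**The case against.** The strongest reply is that nothing goes unreported. Protocol 12.4.6 already plans the same test on everyone dosed, so the dispute is over which of two planned analyses is called primary, in a small Phase II cohort reported with 80% intervals. A full-infusion question is a recognisable one for proof of concept. That stands as mitigation, and it is why the change is cheap. It does not alter the primary result or reconcile the wording.

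Protocol 12.4.4 can be read as applying only after the 12.4.2 restriction, and analysts work from the SAP, which states the completer rule twice. That reading is possible, but the 12.4.4 sentence carries no such qualification.

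Text on the analysis sets is redacted, SAP 7.1 mentions a PD dataset that is not defined in the visible text, and no sensitivity-analysis text is visible in the SAP. Redacted text may add detail. The completer sentences are explicit all the same.

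Some stops may lead to rescue before 90 minutes, so the unassisted rhythm is not always observable. This is correct and calls for a scoring rule.

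The safety set is also formed after randomisation and analysed by treatment received, so it does not restore full randomised protection. That is true, but being dosed precedes any drug effect, whereas completing the infusion does not.

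An all-dosed analysis would count both a participant who stops and the replacement. That changes the denominator but does not in itself create bias.

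Scoring short-monitored non-converters as 'no' is an imputation that could count a recorder failure as a treatment failure. That is also fair, and the sensitivity analysis proposed below addresses it.

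Finally, the illustration crosses 0.05 only under particular assumed counts, and stops within a 15-minute infusion may be few. I agree; the case rests on the text, not on those p-values.

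**Conclusion.** The concern holds and should be fixed. The visible text makes the primary result a completer comparison, although the endpoint is defined from infusion start and can usually be observed after a stop. Protocol 12.4.4 contradicts that rule for a participant who is stopped early but finishes Day 1. The 45-minute condition adds a smaller, outcome-dependent exclusion.

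The direction and size of bias cannot be stated, because the documents give no stopping or conversion rates. Under the assumed counts, two exclusions move the HSY244 rate by about 2 to 8 points in either direction, which is less than the half-width of the 80% interval. The p-value can move across 0.05 in some splits (24 vs 5 with no placebo conversion; 20 vs 9 with one) and does not approach it in others (24 vs 5 or 20 vs 4 with one placebo conversion). The reading of the text itself does not depend on these assumptions.

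**What to change.** 1. Make the all-dosed Fisher analysis of Protocol 12.4.6 (safety analysis set) primary, scored on rhythm to 90 minutes from infusion start whether or not the infusion was finished. Make the completers-only analysis supplementary.
2. Score every dosed participant with no observed conversion as 'no', however long monitored.
3. Report by arm how many were monitored for under 45 minutes. Add a sensitivity analysis that excludes all of them whatever their outcome; Protocol 12.4.5 currently lists none.
4. For the analysis only, and unless redacted text already covers it, state that sinus rhythm first reached after electrical or drug rescue within the 90 minutes is not counted as a conversion.
5. Put this one rule in Protocol 12.4.2 and 12.4.4 and in SAP 6.1.1 and 6.1.3.

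**Cost:** protocol and SAP wording. Both analyses are already planned with the same test and data, so the change swaps their labels and adds two scoring sentences and one small sensitivity analysis. The headline HSY244 conversion rate may be slightly lower. The redacted sample size basis should be checked for any reliance on completers. No clinical stopping or rescue rule changes.

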#### **12.4.3 Handling of remaining intercurrent events of primary estimand**

Not applicable.

#### **12.4.4 Handling of missing values not related to intercurrent event**

Given the short treatment duration in this study, missing data impacting the primary endpoint is expected to be minimal. All participants who complete Day 1 assessments will be included in the primary analysis.

#### **12.4.5 Sensitivity analyses for primary endpoint/estimand**

Not applicable.

#### **12.4.6 Not applicable Supplementary analysis**

As a supplementary analysis, the conversion rates between HSY244 and placebo will again be compared using a Fisher's Exact test. All participants that received any study drug will be included in this analysis (the safety analysis set).

### **12.5 Analysis of secondary endpoints/estimands**

#### **12.5.1 Safety endpoints**

For all safety analyses, the safety set will be used. All listings and tables will be presented by treatment group and cohort.

Safety summaries (tables, figures) include only data from the on-treatment period with the exception of baseline data, which will also be summarized where appropriate (e.g., change from baseline summaries). In particular, tables for adverse events (AEs) will summarize only on-treatment events, with a start date during the on-treatment period (treatment-emergent AEs). The on-treatment period lasts from the date of administration of study treatment to EOS visit.

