#### **4.5.1 Effects on the central nervous system**

GIRK1/4 is closely related to GIRK1/2, which is predominantly expressed in the brain but not the heart. Mice engineered with a knockout of the GIRK2 gene have been reported to be susceptible to stress induced seizures ([Signorini et al 1997](#)). Furthermore, at high doses of BMS 914392, an oral inhibitor of GIRK1/4, subjects reported reversible symptoms of euphoria, ataxia and impaired motor skills ([Podd et al 2016](#)).

Commercially Confidential Information

Commercially Confidential Information

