- For Day 1, 90 min: 1) assess injection/infusion site, 2) assess vital signs, 3) short physical exam, 4) blood draw per assessment schedule, 5) obtain ECG tracing, and 6) after confirmation of persistent AF, initiate direct current cardioversion under appropriate sedation/anesthesia, unless deemed inappropriate by the Investigator. Alternatives to medications listed in the prohibited medication list ([Table 6-2](#)) should be used for sedation/anesthesia, as deemed appropriate by the Investigator.
- For Day 1, 180 min: 1) assess injection/infusion site, 2) assess vital signs, 3) short physical exam, 4) blood draw per assessment schedule, 5) obtain ECG tracing, 6) CCI 7) monitor for adverse events. At this point, the participant can leave the study site to return for assessments at the EOS visit. The observation period can be extended through 24 hours if deemed necessary or appropriate by the Investigator and/or for the convenience of the participant.
- For assessments during other Day 1 time points: 1) assess concomitant medications and therapies, 2) assess injection/infusion site reaction, 3) assess vital signs, 4) blood draw per assessment schedule, and 5) monitor for adverse events.

Blood draws should be obtained at the protocol specified time and within the assessment window as specified in [Table 8-1](#). Every effort should be made for the other assessments (e.g., ECG, vital signs, etc.) to be obtained at the specified assessment time either before or after the blood draw, as described by the order of assessments above.

As per [Section 4.6](#), during a Public Health emergency as declared by Local or Regional authorities, i.e., pandemic, epidemic or natural disaster that limits or prevents on-site study visits, alternative methods of providing continuing care may be implemented by the investigator as the situation dictates. If allowable by a local Health Authority and depending on operational capabilities, phone calls, virtual contacts (e.g., tele consult) or visits by site staff/home nursing staff to the participant's home, can replace on-site study visits, for the duration of the disruption until it is safe for the participant to visit the site again.

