## **10 Safety monitoring and reporting**

### **10.1 Definition of adverse events and reporting requirements**

#### **10.1.1 Adverse events**

An adverse event (AE) is any untoward medical occurrence (e.g., any unfavorable and unintended sign [including abnormal laboratory findings], symptom or disease) in a clinical investigation participant after providing written informed consent for participation in the study. Therefore, an AE may or may not be temporally or causally associated with the use of a medicinal (investigational) product.

The Investigator has the responsibility for managing the safety of individual participant and identifying adverse events.

Novartis Institutes for BioMedical Research qualified medical personnel will be readily available to advise on trial related medical questions or problems.

The occurrence of adverse events must be sought by non-directive questioning of the participant at each visit during the study. Adverse events also may be detected when they are volunteered by the participant during or between visits or through physical examination findings, laboratory test findings, or other assessments.

Adverse events must be recorded under the signs, symptoms, or diagnosis associated with them, accompanied by the following information (as far as possible) (if the event is serious refer to [Section 10.1.2](#)):

1. The severity grade
  - mild: usually transient in nature and generally not interfering with normal activities
  - moderate: sufficiently discomforting to interfere with normal activities
  - severe: prevents normal activities
2. Its relationship to the study treatment. If the event is due to lack of efficacy or progression of underlying illness (i.e., progression of the study indication) the assessment of causality will usually be 'Not suspected.' The rationale for this guidance is that the symptoms of a lack of efficacy or progression of underlying illness are not caused by the trial drug, they happen in spite of its administration and/or both lack of efficacy and progression of underlying disease can only be evaluated meaningfully by an analysis of cohorts, not on a single participant
3. Its duration (start and end dates or ongoing) and the outcome must be reported
4. Whether it constitutes a SAE (see [Section 10.1.2](#) for definition of SAE) and which seriousness criteria have been met
5. Action taken regarding with study treatment.

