These descriptive statistics will be generated for all observations, observations where participants are in AF and observations where participants are in sinus rhythm.

The MMRM and concentration-effect analyses described in Section 6.3.3 may also be used for the ECG parameters described above.

Clinical laboratory evaluations

All laboratory data will be listed by treatment, participant, and visit/time and if normal ranges are available abnormalities will be flagged. A separate listing is provided presenting all parameters in a participant with any abnormal values. Summary statistics will be provided by treatment, visit/time and cohort.

Adverse events

All information obtained on adverse events will be displayed by treatment, participant and cohort.

The number and percentage of participants with adverse events will be tabulated by body system and preferred term with a breakdown by treatment. An adverse event starting in one period and continuing into the next period is counted only in the onset period. A participant with multiple adverse events within a body system and treatment period is only counted once towards the total of this body system and treatment.

The number and percentage of participants with adverse events by maximum severity or severity of adverse events may be tabulated by body system and preferred term with a breakdown by treatment, if deemed necessary.

The number and percentage of participants with serious adverse events may be tabulated by body system and preferred term with a breakdown by treatment, if deemed necessary.

The number and percentage of participants with adverse events classified as related to study drug will be tabulated by body system and preferred term with a breakdown by treatment.

Seizure related adverse events (based on SOC and/or PT) will be listed and summarized separately as AEs of special interest. The number and percentage of participants with such adverse events will be tabulated by body system and preferred term with a breakdown by treatment.

Only adverse events that will occur at or after first drug intake (i.e., treatment emergent AEs) will be included in the AE summaries.

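### The all-cause AE tables pool events before and after response-dependent cardioversion under sedation, so unequal rescue can attenuate, cancel or reverse an HSY244 excess, chiefly for symptomatic CNS events

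*Protocol*

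**What the plan says.** **AE window.** Protocol 12.5.1 limits the AE tables to events "with a start date during the on-treatment period (treatment-emergent AEs"), and defines that period thus: "The on-treatment period lasts from the date of administration of study treatment to EOS visit". End of study is Day 5 (96 hours ± 24 hours). SAP 7.2 has the matching rule: "Only adverse events that will occur at or after first drug intake (i.e., treatment emergent AEs) will be included in the AE summaries". The tables are by treatment. No visible text splits, censors or stratifies them at 90 minutes or at cardioversion.

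**Rescue.** The 90-minute sequence in protocol section 8 ends: "after confirmation of persistent AF, initiate direct current cardioversion under appropriate sedation/anesthesia, unless deemed inappropriate by the Investigator". Sections 3, 6.2.3 and 8.3 word it permissively (it may be applied). Rescue is therefore tied to the primary outcome.

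**Timing data.** Protocol 10.1.1 asks, for each AE: "Its duration (start and end dates or ongoing) and the outcome must be reported". It names no clock time. Section 8.3 does have the investigator record the time of cardioversion.

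**CNS data.** Section 4.5.1 reports that at high doses of another GIRK1/4 inhibitor "subjects reported reversible symptoms of euphoria, ataxia and impaired motor skills". The short exam in section 8.4 checks alertness, orientation, euphoria, involuntary movements and coordination. Table 8-1 marks physical examinations as source documentation only.

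**Related safeguards.** Vital signs and ECG are summarized by treatment and time point (protocol 12.5.1). SAP 7.2 plans separate tables of drug-related AEs and seizure AEs. SAP 6.1.2 reports the proportion electrically cardioverted by treatment.

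**The concern.** A secondary objective is the safety and tolerability of HSY244, and protocol 4.3 gives placebo as the comparison group for safety. Sedation and shock can plausibly produce some of the events being watched for, such as altered alertness, impaired coordination or hypotension. If the drug works, more placebo than HSY244 participants are exposed to them. Their AEs then enter the same all-cause counts as the drug's own, and the more effective the drug, the larger the offset.

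CNS events are the most exposed. Blood pressure, pulse and ECG intervals have pre-shock summaries by time point. The neurological exam has no visible counterpart, so in the visible plan a CNS finding reaches the analysis only if it is recorded as an AE. Dosing, rescue and the 180-minute exam normally fall on one calendar date, so the dates that 10.1.1 requires cannot place an AE before or after the shock. Protocol 12.5.1 also counts a participant once per system organ class, so a pre-shock and a post-shock event in the same class merge in that total.

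**Working it through.** **Inputs from the documents.** The only checkable figures are the Cohort 1 arm sizes; the sample-size section is redacted. At 5:1, 29 randomized gives 29 × 5/6 = 24.2 on HSY244 and 4.8 on placebo, not the stated 20 on HSY244. Twenty on HSY244 leaves 9 of 29 on placebo, or 20/5 = 4 at 5:1. Up to 4 replacements per cohort or redacted text may explain this. The check below therefore uses arms of 24/5, 20/9 and 20/4.

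**Assumed inputs.** The documents give no conversion, rescue or AE rate. Let d be the AE risk before the shock, c the conversion rate and q the AE risk from shock or sedation. Assume that every non-converter is shocked, that no converter is, and that the two AE sources are independent.

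**Simple offset**, (placebo share shocked − HSY244 share shocked) × q:
- Conversion 50% v 5%: (0.95 − 0.50) × 10% / 20% / 40% = 4.5 / 9 / 18 points.
- Conversion 30% v 0%: (1.00 − 0.70) × 10% / 20% / 40% = 3 / 6 / 12 points.

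**Participants with any AE to end of study:** risk = 1 − (1 − d)(1 − (1 − c)q).

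Take d = 20% on HSY244 and 5% on placebo, a true 15-point excess. With conversion 50% v 5% and q = 30%:
- HSY244: 1 − 0.80 × (1 − 0.50 × 0.30) = 1 − 0.80 × 0.85 = 32.0%
- Placebo: 1 − 0.95 × (1 − 0.95 × 0.30) = 1 − 0.95 × 0.715 = 32.1%
- Difference: −0.1 points

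HSY244 minus placebo in the table to end of study, in points, with placebo conversion at 5%:

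| HSY244 conversion | q = 10% | q = 30% | q = 50% |
|---|---|---|---|
| 5% (equal rescue) | +13.6 | +10.7 | +7.9 |
| 30% | +11.6 | +4.7 | −2.1 |
| 50% | +10.0 | −0.1 | −10.1 |
| 70% | +8.4 | −4.9 | −18.1 |

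The excess vanishes at q = 0.15 / [0.95 × 0.95 − 0.80 × (1 − c)], where c is HSY244 conversion: 44%, 30% and 23% for conversion of 30%, 50% and 70%. With equal rescue the excess shrinks but stays positive.

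**At this trial's size.** By exact binomial enumeration, this is the chance that the placebo AE proportion equals or exceeds the HSY244 proportion (conversion 50% v 5%, q = 30%):

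| Arms (HSY244/placebo) | 0-90 minute table | Table to end of study |
|---|---|---|
| 24/5 | 12.0% | 47.2% |
| 20/9 | 11.6% | 48.1% |
| 20/4 | 16.1% | 51.5% |

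The 0-90 minute column assumes that the drug's excess arises before the shock.

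**The case against.** The case against has force on several points.

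- **Cardiovascular effects.** A reader might infer that cardiovascular harm in general is hidden. The documents do not support that. Table 8-1 schedules vital signs at 0, 5, 10, 15, 30, 60 and 90 minutes and ECGs at 0, 30 and 90 minutes, with the 90-minute assessments completed before any shock. SAP 7.2 also gives ECG statistics by rhythm. These are already pre-rescue comparisons by arm.
- **Other AE tables.** Not every AE table is a plain all-cause count. The drug-related and seizure tables give a further view. They are partial safeguards: attribution is blinded, and reduced alertness after sedation is easily put down to the sedative.
- **Timing data.** A reader might infer that events can never be ordered against the shock. That is not shown. Section 10.1.1 requires end dates as well as start dates, and the eCRF is not supplied. Screening and dosing may share a day, so applying the treatment-emergent definition already needs more than a date. A time or a before/after-dose flag may therefore exist.
- **The full-period count is legitimate.** Section 4.5 names avoiding cardioversion and sedation as a potential benefit, so counting all AEs regardless of rescue answers a real question. No formal AE test is planned, and the stopping rules do not use arm differences.
- **Precision.** With roughly 4 to 9 placebo participants, any AE contrast is imprecise, with or without a split.

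What stands is that no visible all-cause AE comparison is free of planned rescue, and symptomatic CNS events have no other visible route into the analysis.

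**Conclusion.** The concern holds for the all-cause AE tables, chiefly for symptomatic CNS-type events. If HSY244 converts more participants than placebo, these tables can attenuate, cancel or reverse a true excess. In the worked case 15 points become −0.1; across the unequal-conversion cases tabulated, the result runs from +11.6 to −18.1.

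These sizes rest wholly on assumed conversion and rescue-AE rates. They also assume that every non-converter is shocked, although rescue is discretionary, and that no one who converts briefly and relapses is shocked. If conversion is equal in the arms, there is dilution but no imbalance bias. A reader might infer that masking will occur; the documents support only that it can. It is a gap worth closing because closing it is cheap.

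**What to change.** 1. Confirm that the AE eCRF captures onset time for Day 1 events; if it does not, add the field.
2. Add to protocol 12.5.1 and SAP 7.2 an AE summary by treatment for events starting 0-90 minutes after the start of infusion and before any cardioversion. This window is common to both arms and precedes planned rescue, so it keeps the randomized comparison. Footnote any shock given earlier for a new arrhythmia (section 6.2.3).
3. Keep the table to end of study. Which of the two should lead is open to debate; showing both is enough.
4. Optionally, list later events by cardioversion status and label this as descriptive. Cardioversion status arises after randomization, so that split is not a randomized comparison.

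**Cost.** At most one eCRF field and one or two tables, with no new visits or procedures. The 0-90 minute table will hold few events in about 29 participants with a small placebo arm, and late drug effects will appear only in the full-period table.
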